41	Section 14.3— Completion of Electronic Case Report Forms (eCRFs)	
Under 1st paragraph, 2nd and 3rd sentences:                      The eCRFs will be reviewed by the Sponsor's designated clinical monitor; and then transmitted by the monitor to the Contract Research Organization's (CRO) electronic database. All data entered into the eCRF should be verifiable with source documents unless the eCRF is the source itself.
 
Under 2nd paragraph:                      To ensure the quality and integrity of the data, it is the responsibility of the Principal Investigator or designee to in a timely manner, enter data into the eCRFs for each enrolled subject in a timely manner, who is enrolled to participate in this study. GEHC will provide eCRFs and will train study staff on data entry using Good Documentation Practices (GDP). eCRF completion guidelines may be provided by the Sponsor to help facilitate training. eCRFs will be completed as information becomes available.
 
Under 4th paragraph:                      During the course of monitoring, if any errors or omissions are found, they shall be brought to the attention of the site designee, who shall make the corrections, as appropriate on the eCRFs. In the event of an eCRF audit or data review once the eCRFs have been pulled from the site completed, a data query Data Clarification Form (DCF) will be generated and the error, omissions or clarifications will be corrected on these associated eCRF forms.
 
Under 5th paragraph:                      The Principal Investigator or a Sub-Investigator will electronically sign and date the indicated places on the eCRF. This signature will indicate that a thorough inspection of the data has been made and will thereby certify the contents of the form.
	The correction was made to be consistent with the type of data collection system that will be used in the study, and does not impact the study design or risk.
42	Section 14.4—Data Handling and Record Keeping	All documents and data shall be produced and maintained in a manner that assures control and traceability.	Administrative change.

**Study Title:** Multi-site Anesthesia randomized controlled Study of End tidal control (Et Control) compared to conventional anesthesia Results (MASTER-Anesthesia Trial)  
**Study No:** 123.07-2015-GES-0002

Item	Section	Revision or Clarification	Justification				
43	Section 14.5—Record Retention at the Site	
Under 1st paragraph, 1st and 2nd sentences:
 
All records pertaining to the conduct of the study, including source data, e-CRFs, electronic data ICFs, IRB correspondence, and other study documentation must be retained at the site for inspection at any time by the Sponsor's authorized Study Monitor or designee or regulatory agency; i.e., US Food and Drug Administration (USFDA). These records will be maintained by the site for a minimum of 2 years, per US FDA 21 CFR Part 812.140(d), or a maximum of 3+ years, according to the Sponsors policies; after the investigation termination date or after the date the records are no longer required for purposes of supporting a premarket approval application or notice of completion of a product development protocol.
 
Under the 1st, 2nd, and 3rd bullets in the 1st paragraph:
 
 
▪ Source data and documentation: relevant to data recorded for subject screening and eCRF corroboration (i.e., information in original records, certified copies of original records of clinical findings, observations, or other activities for the study)
 
▪ Subject Files: containing the eCRF worksheets and completed patient eCRFs
 
▪ Regulatory Binder: containing the protocol and amendments, IRB submissions and approvals, blank and signed/dated ICF(s), and site study logs
 
	Administrative change.				
44	Section 16—Publication Policy	
Under 2nd paragraph, 1st sentence:
 
Data obtained from this study may be used for submission to peer reviewed publications that are consistent with study contracts with prior permission from GE Healthcare.
	Administrative change.				
45	Section 18—Glossary of Terms	
The following terms and definitions were added:
 
 
 Adverse Device Effect (ADE)	An adverse event related to the use of an investigational medical device [ISO 14155:2011 3.1]. This includes any adverse events resulting from insufficient or inadequate instructions for use, deployment, implantation, installation, or operation, or any malfunction of the investigational medical device. This includes any event that is a result of a user error or intentional misuse of the investigational device [ISO 14155:2011 3.43].	
 
 Adverse Event (AE)	As defined by EN ISO 14155-2011: any untoward	
 
	Adverse Device Effect (ADE)	An adverse event related to the use of an investigational medical device [ISO 14155:2011 3.1]. This includes any adverse events resulting from insufficient or inadequate instructions for use, deployment, implantation, installation, or operation, or any malfunction of the investigational medical device. This includes any event that is a result of a user error or intentional misuse of the investigational device [ISO 14155:2011 3.43].	Adverse Event (AE)	As defined by EN ISO 14155-2011: any untoward	This is a clarification that does not impact the study design or risk.
Adverse Device Effect (ADE)	An adverse event related to the use of an investigational medical device [ISO 14155:2011 3.1]. This includes any adverse events resulting from insufficient or inadequate instructions for use, deployment, implantation, installation, or operation, or any malfunction of the investigational medical device. This includes any event that is a result of a user error or intentional misuse of the investigational device [ISO 14155:2011 3.43].						
Adverse Event (AE)	As defined by EN ISO 14155-2011: any untoward						

**Study Title:** Multi-site Anesthesia randomized controlled Study of End tidal control (Et Control) compared to conventional anesthesia Results (MASTER-Anesthesia Trial)  
**Study No:** 123.07-2015-GES-0002

Item	Section	Revision or Clarification	Justification
		
medical occurrence, unintended disease or injury, or untoward clinical signs (including abnormal laboratory findings) in subjects, users or other persons, whether or not related to the investigational medical device.
 
Anticipated Adverse Device Effect
 
Clinician
 
Device deficiency
 
Early termination of a subject
 
Heart rate
 
Non-Invasive Blood pressure (NIBP)
 
Non rebreathing system
 
Peripheral Capillary Oxygen Saturation (SpO2)
 
Post-anesthesia discharge time
	
		
Any adverse event and/or reaction, the specificity or severity of which is consistent with the IRB approved informed consent, protocol, investigator brochure, or product labeling.
 
Specialty clinician trained in the administration of anesthesia care, including anesthesiologists, residents, fellows, CRNA, <del>and/or certified Anesthesia Assistant.</del>
 
An inadequacy of a medical device with respect to its identity, quality, durability, reliability, safety, or performance, such as malfunctions, use errors, and inadequate labelling [ISO 14155:2011 3.15].
 
Any situation in which the clinician determines they no longer want to continue with the case, or the clinician may choose to discontinue the Et Control mode during a case.
 
Defined as the heart rate < 45bpm or > 110bpm for more than 5 minutes.
 
Defined as having the systolic blood pressure (SBP) reading < 80 mmHg or > 160 mmHg or mean arterial pressure (MAP) of <60 mmHg or > 120 mmHg for >10 minutes.
 
A breathing system where the patient inspired gases <del>are</del> totally supplied by the gas mixer and the vaporizer.
 
Defined as having a value less than 90% for more than 5 minutes.
 
From the OR discharge to discharge time from the PACU.
	

**Study Title:** Multi-site Anesthesia randomized controlled Study of End tidal control (Et Control) compared to conventional anesthesia Results (MASTER-Anesthesia Trial)  
**Study No:** 123.07-2015-GES-0002

Item	Section	Revision or Clarification	Justification
		
 Serious Adverse Device Effect (SADE)                      An adverse device effect that has resulted in any of the consequences characteristic of a serious adverse event [ISO 14155:2011 3.36].                 
 
 Serious Adverse Event (SAE)                      As defined by EN ISO 14155 – 2011: an adverse event that                     
 
d. led to death;
 
e. led to a serious deterioration in the health of the subject, that either resulted in:                             
 
(5) a life-threatening illness or injury, or
 
(6) a permanent impairment of a body structure or a body function, or
 
(7) in-patient or prolonged hospitalization, or
 
(8) medical or surgical intervention to prevent life-threatening illness or injury or permanent impairment to body structure or a body function;
 
 
 
f. led to fetal distress, fetal death or a congenital abnormality or birth defect.
 
 
 
 Unanticipated adverse device effect (UADE)                      As defined by 21 CFR 812.3: means any serious adverse effect on health or safety or any life-threatening problem or death caused by, or associated with, a device, if that effect, problem, or death was not previously identified in nature, severity, or degree of incidence in the investigational plan or application (including a supplementary plan or application), or any other unanticipated serious problem associated with a device that relates to the rights, safety, or welfare of subjects.                 
 
 Unanticipated serious adverse device effect (USADE)                      A serious adverse device effect, which by its nature, incidence, severity, or outcome has not been identified in the current version of the risk analysis report [ISO 14155:2011 3.42]. In the United States, any serious adverse effect on health or safety or any life-threatening problem or death caused by, or associated with, a device, if that effect, problem, or                 
	

**Study Title:** Multi-site Anesthesia randomized controlled Study of End tidal control (Et Control) compared to conventional anesthesia Results (MASTER-Anesthesia Trial)  
**Study No:** 123.07-2015-GES-0002

Item	Section	Revision or Clarification	Justification
		
death was not previously identified in nature, severity, or degree of incidence in the study documents, will be reported in accordance with 21 CFR §812.3 and applicable laws and regulations.
 
Unrecoverable failure      The inability to use Et Control mode because of unrecoverable device malfunction
	
46	Appendix 3—Study Schedule of Procedures	
The following procedures were added:
 
Surgical History – marked screening column
 
Concomitant Medications – marked screening column
 
Current Surgery – marked screening column
 
Height / Weight / BMI – marked screening column
 
Time of Induction – marked induction and intubation column
 
Time of Intubation – marked induction and intubation column
 
Time of admission to ICU or general ward – marked PACU discharge column
 
User Survey  – marked emergence phase column
 
The following procedure was corrected:
 
Mean Arterial Pressure (MAP) – added a mark under the screening column
 
The added footer #6 is as follows:
 
6 User survey to be completed after the emergence phase for each case.
	
These are clarifications that conform to the procedures stated in this protocol, and do not impact the study design or risk.

**Study Title:** Multi-site Anesthesia randomized controlled Study of End tidal control (Et Control) compared to conventional anesthesia Results (MASTER-Anesthesia Trial)  
**Study No:** 123.07-2015-GES-0002

Item	Section	Revision or Clarification		Justification	
		
Under the heading, the last column was corrected to reference the added footer:                      24 HR POST OPERATIVE #
 
The added footer #4 is as follows:  4 There will be no follow-up visit after the 24-hour Post-Operative period.
 
The following was corrected to reference the added footer:                      Adverse Event Assessment #
 
The added footer #5 is as follows:  5 Adverse Event Assessment will be performed from the time the subject provided consent to the end of study participation.
 
The following statement after the table for Appendix 3 was deleted, which was replaced by footers #4 and #5:  <del>* Subjects will be followed for AE reporting purposes from the time they provided consent to the end of the study. There will be no follow-up visit after the 24 hour Post-Operative period.</del>
		
These are clarifications that do not impact the study design or risk.
	
47	Appendix 4—Study Site and Investigator List	
Investigator(s):
 
To be determined prior to start of study. (add/remove rows, as necessary, to account for all sites)
	
Investigator Name, Title/Credentials, and role (e.g. Principal Investigator, Sub-investigator, Co-investigator, etc.)                      Tel: X-XXX-XXX-XXXX                      e-mail: [contact]
	
Site Name                      Address: Address Line 1                      Address Line 2
	
This is a clarification that does not impact the study design or risk.

**Study Title:** Multi-site Anesthesia randomized controlled Study of End tidal control (Et Control) compared to conventional anesthesia Results (MASTER-Anesthesia Trial)  
**Study No:** 123.07-2015-GES-0002

Item	Section	Revision or Clarification		Justification	
			Investigator Name, Title/Credentials, and role (e.g. Principal Investigator, Sub- investigator, Co-investigator, etc.) Tel: X-XXX-XXX-XXXX e-mail: [contact]	Site Name Address: Address Line 1 Address Line 2	
			Investigator Name, Title/Credentials, and role (e.g. Principal Investigator, Sub- investigator, Co-investigator, etc.) Tel: X-XXX-XXX-XXXX e-mail: [contact]	Site Name Address: Address Line 1 Address Line 2	
48	Appendix 5— Amendments (Protocol Version 1.0 to 2.0)	
A detailed amendment is provided for version 1.0 to version 2.0. Version 1.0 was the first version submitted to the U.S. Food and Drug Administration (US FDA) for the Investigational Device Exemption (IDE) submission, and was not provided to the investigational sites for IRB approval.
 
Purpose of Amendment:
 
 
4) To make changes as requested by the US FDA, per FDA IDE deficiencies and disapproval letter dated 14/Jul/2016, per IDE #G160132.
 
5) Sponsor administrative changes.
 
6) To make general typographical/formatting corrections, in accordance with current standard style guides, American Medical Association (AMA) style, and internal standards of the Sponsor.
 
 
These changes are not expected to increase subject or operator risk or to adversely impact the scientific integrity or conduct of the study.
 
In the table below, point-by-point revisions are shown as additions in double-underline (double-underline) and deletions in strikethrough (<del>strikethrough</del>) for each change made in this amendment from the previous version.
 
(NOTE: In the protocol under this section, this table of point-by-point revisions is inserted after the above paragraphs.)
		
This section has been added to list the above-mentioned changes made to the protocol from version 1 to version 2.
	

**Study Title:** Multi-site Anesthesia randomized controlled Study of End tidal control (Et Control) compared to conventional anesthesia Results (MASTER-Anesthesia Trial)  
**Study No:** 123.07-2015-GES-0002

GE Healthcare

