### 1.2.3 Human Studies – under U.S. FDA 21 CFR Part 812–Investigational Device Exemption (IDE)

A feasibility clinical study with human subjects was performed from 24/Feb/2014 to 30/Sep/2014 under the U.S. Food and Drug Administration (FDA) 21 Code of Federal Regulation (CFR) Part 812—Investigational Device Exemption (IDE) (*Study Title: Single Site, Randomized, Controlled Feasibility Study with and without Smartflow for Routine Anesthesia [Smartflow™ Feasibility], Study No. 123.01-2013-GE5-0001, FDA IDE No. G120300*). The purpose of this feasibility study was to collect and analyze safety and efficacy data on the investigational Et Control (formerly called as Smartflow) option to support the design of this pivotal clinical study. In this feasibility study, the Et Control option was used with the Aisys Anesthesia System, which was intended to provide general inhalation anesthesia and volume or pressure control ventilation support. There is no difference between Smartflow and Et Control (only a name change).

There were two arms in the study – Et Control (Smartflow) Arm (Aisys with Et Control) and the Control Arm (Aisys without Et Control). The study was conducted at University of Iowa Hospital and Clinics in Iowa City, Iowa, USA, and had a total of 28 evaluable subjects – 15 subjects in the Et Control Arm (6 females and 9 males) and 13 subjects in the Control Arm (9 females and 4 males). Results from the 28 evaluable subjects related to safety and efficacy were reported according to adverse events, Et Control performance, and comparison between the Et Control Arm and the Control Arm. Clinicians experiences in using the Et Control option were also reported.

There were no serious adverse events or deaths reported. Nine adverse events of hypotension were reported (6 were reported from the Et Control (Smartflow) Arm and 3 from the Control Arm). All events were anticipated and were considered hypotension. All events were determined by the clinician to likely not be related to the device or Et Control. All events were treated with medication, and resolved without sequelae.

Results showed evidence that Et Control (Smartflow) was able to successfully maintain and adjust settings in response to clinician selections, within a performance range equivalent to or potentially better than the Control Arm. Results also indicated that Et Control may reduce the duration of large deviations from the intended steady state settings.

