### 4.2 Controls and Minimization of Bias

All reasonable attempts will be made to control and minimize bias during this study, including the following:

- Consecutive enrollment of subjects will be employed to limit selection bias.

**Study Title:** Multi-site Anesthesia randomized controlled Study of End tidal control (Et Control) compared to conventional anesthesia Results (MASTER-Anesthesia Trial)  
**Study No:** 123.07-2015-GE5-0002

GE Healthcare

- Subjects will be randomized in a single-blind method to either the Et Control Arm or the Control Arm.
- Subjects will be blinded to their assignment; however, given the nature of the use of the investigational Et Control option during a case, the clinicians and Investigators cannot be blinded to the subject groups.
- Quotas or stratification criteria will be employed to ensure equitable distributions of patients and thus reduce spectrum bias.
- Multiple sites will be used to provide a broader cross-section of the population of patients and clinical practices, and thus reduce spectrum bias

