### 6.3.2 Operative Procedure Data Collection (Induction/Intubation, Maintenance, and Emergence)

The following information will be collected from each subject case.

- ◆ Collect the following data from the departmental electronic medical record (EMR) from induction through emergence phase:

**NOTE:** *Collection of vital signs shall be made at a minimum of every 2.5 minutes for the first 2 hours of each case, and at a minimum of every 5 minutes thereafter through the emergence phase. If the subject becomes unstable, the clinician shall revert to collecting the vital signs at a minimum of every 2.5 minutes, and shall record the reason for change in the collection of vital signs and any adverse events that may occur. Once the subject returns to a stable state, the clinician shall collect the vital signs at a minimum of every 5 minutes.*

1. Heart Rate
  2. Blood Pressure (systolic and diastolic)
  3. Mean Arterial Pressure (MAP)
  4. Peripheral Capillary Oxygen Saturation (SpO2)
- ◆ Record the following data on the eCRFs throughout the study:
    1. Concomitant Medications: Intravenous medications [name, dose, time administered, time stopped, and rate (if applicable); including intravenous anesthetic agents used prior to intubation] administered from pre-OP through emergence phase
    2. Vasoactive medications: (e.g., Ephedrine, Epinephrine, Dopamine, Norepinephrine, Phenylephrine, etc.) including name, dose and unit, rate, time administered, time stopped, and reason for dose (prophylactic, hypotension, anesthetic overdose, hypovolemia, depressed cardiac output, depressed systemic vascular resistance, dose decrease or other) – administered from induction to emergence phase
    3. Anesthetic agents used prior to intubation (*Note: Record inhaled and intravenous anesthetic agent used prior to intubation. Intravenous anesthetic agent should be recorded in the Intravenous Medication During Study eCRF.*)
    4. Time of induction
    5. Time of intubation
    6. Operative positioning (*record the primary operating position*)
    7. Incision time

**Study Title:** Multi-site Anesthesia randomized controlled Study of End tidal control (Et Control) compared to conventional anesthesia Results (MASTER-Anesthesia Trial)  
**Study No:** 123.07-2015-GE5-0002

GE Healthcare

8. Estimated blood loss
  9. End time of surgery (*often defined as the procedure end time, last stitch, or placement of the last bandage*)

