### 8.1.7 Analysis of Adverse Events

Adverse events will be observed and recorded. Percent of subjects with AEs will be calculated, and comparisons between groups will be performed using Fisher exact test. Number of AEs and AE event rate will also be analyzed using non-parametric Wilcoxon method.

Analysis will be performed for a subset of adverse events of vital sign abnormalities including non-invasive blood pressure (NIBP), SpO2, and heart rate.

In addition, analysis of adverse events will be performed for each subset of patients defined by the pre-existing hypertension (*defined as a patient treated for hypertension*) status and ASA status.

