### 8.1.8 Analysis of Vasoactive Medication Use

When vasoactive medication is used during the anesthesia procedure, the medication name, reason for use, amount used, duration of use will be recorded. Usage of vasoactive medication will be analyzed for the Et Control and the Control Arms in terms of types of vasoactive medication used, reason for use, number of subjects and total dose. The

**Study Title:** Multi-site Anesthesia randomized controlled Study of End tidal control (Et Control) compared to conventional anesthesia Results (MASTER-Anesthesia Trial)  
**Study No:** 123.07-2015-GE5-0002

GE Healthcare

vasoactive medication use will be analyzed by ASA status and by preexisting hypertension status. Comparison for categorical variables will be performed using Fisher exact test and comparison for numerical variables will be performed using Wilcoxon rank-sum method.

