**Table 10-1 – Anticipated Adverse Events and Device Effects**

Event	Machine Failure	General Anesthesia	Aisys CS 	Et Control
Hypoxia	Insufficient oxygen delivery	x	x	x
	Incorrect oxygen concentration of fresh gas flow	x	x	x
	Insufficient ventilation	x	x	x
Hyperoxia	Excessive oxygen delivery	x	x	x
Cardiac Arrest	Incorrect anesthetic agent delivery	x	x	x
Intra-operative Awareness	Insufficient AA delivery	x	x	x
Hypertension	Insufficient anesthetic agent delivery	x	x	x
Hypotension	Excessive anesthetic agent delivery	x	x	x
Airway Fire	Electro-cautery in airway with high O 2	x	x	x

Adverse event assessment will be conducted from the time the subject provided consent to the end of the subject's participation in the study.

There is always a chance of unexpected risks. Throughout the study, the Sponsor will evaluate and update safety information in study documents.

**Study Title:** Multi-site Anesthesia randomized controlled Study of End tidal control (Et Control) compared to conventional anesthesia Results (MASTER-Anesthesia Trial)  
**Study No:** 123.07-2015-GE5-0002

GE Healthcare

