		
Under the 2nd bullet, item #2, 4 and 5:
 
2. Vasoactive medications: (e.g., Ephedrine, Epinephrine, Dopamine Norepinephrine, Phenylephrine, etc.) including name, dose and unit, rate, time administered, time stopped, and reason for dose (<del>standard of care</del>prophylactic, hypotension, anesthetic overdose, hypovolemia, depressed cardiac output, depressed systemic vascular resistance, dose decrease or other) – administered from induction to emergence phase
	
This is a clarification of data collection and in response to Question #4 under the section “Additional Recommendations and Considerations—Study Design Considerations” of the IDE deficiencies and disapproval letter dated 14/Jul/2016 from the FDA for IDE #G160132.

		
Under the 2nd bullet, item #4 and 5:
 
4. Time of induction
 
5. Time of intubation
 
9. End time of surgery (often defined as the last stitch or placement of the last bandage)
	
This is a clarification that includes data collected on the electronic case report form, and does not impact the design of the study design or risk.

20	Section 6.3.4—Twenty-four (24) hours Post PACU Data Collection	
First sentence:
 
Collect the following information 24-hours post PACU discharge for subjects that completed the study and those that were withdrawn or discontinued from study participation during the study procedure.
	
The is a clarification that conforms to Section 11.3 of the protocol, and does not impact the study design or risk.

21	Section 6.4—Withdrawal	
The following paragraph was moved to a new section 11.3—Follow-up and Use of
	
This is a clarification that consolidates relevant

**Study Title:** Multi-site Anesthesia randomized controlled Study of End tidal control (Et Control) compared to conventional anesthesia Results (MASTER-Anesthesia Trial)  
**Study No:** 123.07-2015-GE5-0002

Item	Section	Revision or Clarification	Justification

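### The reasons for vasoactive doses overlap and Section 8.1.8 names no pooled count of subjects treated for low blood pressure, so the supportive by-reason comparison can lose power or reflect labelling

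*Combined protocol and SAP*

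**What the plan says.** Section 6.3.2, item 2 under the eCRF data, asks for a "reason for dose (prophylactic, hypotension, anesthetic overdose, hypovolemia, depressed cardiac output, depressed systemic vascular resistance, dose decrease or other". The version 1.0 to 2.0 changes in Appendix 5 (item 19) carry the same list, ending "anesthetic overdose, hypovolemia, depressed cardiac output, depressed systemic vascular resistance, dose decrease or other", so the wording is current. No label is defined, no order of precedence is given, and nothing says whether one or several reasons may be recorded for a dose.

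Section 8.1.8 analyses vasoactive use by arm "in terms of types of vasoactive medication used, reason for use, number of subjects and total dose", also by ASA and hypertension status. On the test it says: "Comparison for categorical variables will be performed using Fisher exact test". It gives no significance level and no pooled category.

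Section 4.2 states that "the clinicians and Investigators cannot be blinded to the subject groups". Table 10-1 pairs the event hypotension with the failure "Excessive anesthetic agent delivery".

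Section 8.1.7 adds a check that does not use these labels: "Analysis will be performed for a subset of adverse events of vital sign abnormalities". Its low-pressure event is defined in Section 10.2 by systolic pressure below 70 mmHg or mean arterial pressure below 55 mmHg for more than 5 minutes. Other physiological changes may be reported at the clinician's discretion.

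**The concern.** The list mixes two questions: what was treated, and what was thought to cause it. A dose given for low pressure could be recorded as hypotension or as anesthetic overdose, and Table 10-1 itself connects those two. Hypovolemia, depressed cardiac output and depressed systemic vascular resistance also read as causes of low pressure, although that is a clinical reading and not something the protocol states. The choice among the labels is made by someone who knows the arm.

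The other planned summaries do not supply the missing count:

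- Any use of a vasoactive drug does not depend on the label, but it mixes treatment with prophylaxis.
- Drug type and total dose do not isolate treatment of low pressure.
- The Section 10.2 threshold event does not capture a fall corrected within 5 minutes. Such a fall enters the adverse event data only at the clinician's discretion.

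Treated hypotension is a natural safety measure here. In the feasibility study (Section 1.2.3) there were nine hypotension events, six in the Et Control arm (15 subjects) and three in the Control arm (13 subjects), and "All events were treated with medication, and resolved without sequelae". What is at stake is how the vasoactive table can be read: a real excess could be spread thinly over labels, or a difference in labelling could look like a difference in safety.

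**Working it through.** The documents give no rate, power or sample size for the vasoactive comparison, so what follows is an illustration.

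**Sample size.** The plan's own figure reproduces. For EtAA (Table 8-1: margin 5, SD 16, expected difference 90 − 87 = 3, one-sided 0.025, power 0.95), a two-sample t calculation needs 105 per arm. Then 105 / (1 − 0.15) = 123.5, rounded up to the stated 124. I use n = 124 per arm.

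**Method.** The exact rejection probability of Fisher's test (two-sided, p ≤ 0.05) is the sum, over all outcomes (x, y) that reject, of Bin(x; 124, p_C) × Bin(y; 124, p_E).

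**Assumptions.** Treated-hypotension rates are taken from feasibility events per subject: p_C = 3/13 = 23.1% and p_E = 6/15 = 40%. These are adverse events, not subjects given a vasopressor, so they are only a stand-in. I also assume one label per subject and a separate 2×2 test for each label. The label shares are my own.

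**1. Splitting that is equal in both arms (label rate = share × treated rate)**

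| Comparison | Control | Et Control | Power |
|---|---|---|---|
| Pooled | 23.1% | 40.0% | 0.79 |
| Label holding 80% of treated subjects | 18.5% | 32.0% | 0.64 |
| Label holding 50% | 11.5% | 20.0% | 0.38 |
| Label holding 20% | 4.6% | 8.0% | 0.12 |

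**2. Any use in place of treated use.** With independent prophylactic use at rate q in both arms, the any-use rate is p + (1 − p)q.

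- q = 20%: 38.5% vs 52.0%, power 0.52.
- q = 40%: 53.8% vs 64.0%, power 0.32.

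**3. Unequal labelling with no true difference (40% treated in both arms).** The label rate is 0.40 × the share of treated subjects given that label.

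| Share, Control vs Et Control | Label rates | Probability of p ≤ 0.05 |
|---|---|---|
| 20% vs 5% | 8% vs 2% | 0.47 |
| 20% vs 10% | 8% vs 4% | 0.17 |
| 15% vs 10% | 6% vs 4% | 0.06 |

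A count pooled over the low-pressure labels, with each subject counted once, does not change when doses move among those labels.

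**4. What pooling does not cure.** Suppose 60% receive a vasoactive drug in both arms, and 80% of them in one arm but 60% in the other are labelled as treated rather than prophylactic. The pooled rates become 0.60 × 0.80 = 48% and 0.60 × 0.60 = 36%, and p ≤ 0.05 occurs in 42% of trials although drug use is equal.

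**The case against.** The strongest reply is that no decision rests on this table. The test sequence in Section 8.1.2 is the primary endpoints, agent usage, user interaction and time to OR discharge. The pass rule in Section 8.4 uses only EtAA and EtO2, and the safety endpoint in Section 3.4.2 is adverse events. That stands in full: the 47% is not an error rate for any planned conclusion.

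The tested form is also assumed. Section 8.1.8 does not specify a 2×2 test per label, and reasons are recorded per dose, so one subject may fall under several. If several reasons are allowed, the problem becomes double counting rather than splitting. This limits the figures but does not remove the overlap.

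The plan also has checks on over-delivery that do not use these labels: overshoot counts (Section 8.1.4.1), delivered EtAA and its deviation around an adverse event (Section 8.1.9) and threshold-defined vital-sign events (Section 8.1.7). These reduce the weight of the point. None of them counts subjects treated for low pressure.

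A reader might go further in four ways that the documents do not support:

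- **That hypotension is the characteristic over-delivery harm of Et Control.** Table 10-1 marks it equally for general anesthesia, Aisys CS² and Et Control. All nine feasibility events were judged likely unrelated to the device, and 6/15 vs 3/13, even read as subjects, gives Fisher p = 0.43.
- **That treated low pressure is not counted at all.** Hypotension is one of the reasons, and reason and number of subjects are both analysed. What is missing is the pooled count.
- **That a promptly treated fall can never become an adverse event.** It can, at the clinician's discretion.
- **That pooling removes the bias.** Step 4 of the working shows that it does not.

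**Conclusion.** The point holds as a modest one. The reason labels overlap, they are undefined, and unblinded clinicians choose them. Section 8.1.8 compares arms on them without a pooled count of subjects treated for low pressure. At 124 per arm and the assumed 23% vs 40%, reading a single label instead of the pooled count takes power from 0.79 to between 0.64 and 0.12. With equal true rates, a spurious label difference appears in 6% to 47% of trials, depending on the size of an assumed labelling gap. The 47% needs a fourfold gap, for which the documents give no evidence.

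These sizes depend on assumed rates and shares, one label per subject and one test per label. The overlap of anesthetic overdose with hypotension follows from Table 10-1; for the other three labels it is a clinical reading. The consequence is confined to a supportive safety analysis. This is a worthwhile, cheap improvement and no threat to the trial's main conclusions.

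**What to change.** In Section 8.1.8, prespecify as the main vasoactive comparison the number of subjects with at least one dose recorded for hypotension, anesthetic overdose, hypovolemia, depressed cardiac output or depressed systemic vascular resistance. Pool these reasons, count each subject once, and give the risk difference with its 95% CI.

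- Report prophylactic use separately and any use as a sensitivity analysis, because the pooled count does not remove misclassification between prophylaxis and treatment.
- Keep single reasons descriptive, and compare total dose only within the same drug.
- Define the labels briefly, and state on the eCRF whether several reasons may be recorded for one dose.

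The cost is a change of SAP wording, a short eCRF instruction and one extra table from data already collected. Single reasons would no longer be formally tested.

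Separately, the systolic threshold for the blood pressure event is below 70 mmHg in Section 10.2 and below 75 mmHg in the Glossary. The sponsor must reconcile the two, since the vital-sign event analysis in Section 8.1.7 depends on that definition.
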